#### **5.4.9.10. Recurrent episodes of RIP and PPS during the study**

The numbers of subjects with recurrent pericarditis episodes will be summarized by the number of recurrent episodes during the study. Duration-adjusted number of episodes will be defined for each subject as the number of recurrent episodes during the study divided by the study duration (from the first dose of the study drug to study completion/discontinuation) in years. Duration-adjusted number of episodes will be summarized descriptively. This analysis will be performed for the mITT population.

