**Extension Period (EP):** The EP is defined as the 18 weeks following the Treatment Period. Subjects who are considered to be “Treatment Responders” will be, at the discretion of the Investigator, offered participation in an optional 18-week EP, in which weekly administration of open-label KPL-914 may be continued for a total duration of 24 weeks. The weekly KPL-914 doses will be by self-administration or administered by adequately trained caregiver, and study nurse visits to the subject’s home as well as Investigator (or designee) telephone calls/virtual visits will continue on a monthly basis. During the EP, the Investigator is encouraged to wean concomitant NSAIDs, and/or colchicine, and/or corticosteroids. It is encouraged that NSAIDs and colchicine be tapered and withdrawn within 15 days after entry into the EP. It is encouraged that corticosteroids be progressively tapered (e.g., by 5 mg prednisone or equivalent every week in adults or 0.2mg/kg every week in subjects <18yo) and discontinued within 6 weeks after entering to EP (i.e., by Study Week 12) unless in the opinion of Investigator, a different corticosteroid weaning schedule is required based on subject’s clinical status. Other pericarditis medications may also be initiated at the discretion of the Investigator. All changes to pericarditis-related medications should be captured in the source records and eCRF

Unscheduled clinic visits can be scheduled any time as determined by the Investigator/upon subject request. In addition, Investigators are encouraged to schedule subjects at the Study Site/Clinic for an in-person Interval Evaluation Visit between Weeks 15 to 20 (8 to 13 weeks after Visit 7) to assist the Investigator in the clinical management of the subject. During this visit a physical examination, vital signs, ECG, echocardiogram, and laboratory testing can be performed. However, this visit is not mandatory, and therefore not all subjects will have it.

Subject-reported pericardial pain evaluations using a validated 11-point NRS instrument as well as AE monitoring will be performed during the EP at on-site clinic visits and/or during monthly Investigator (or designee) phone calls/virtual visits. A subject-reported QoL questionnaire will be administered at the Interval Evaluation Visit and the Final Visit of the EP. At the end of the EP, subjects will complete the Week 25/Final Visit.

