### **5. STATISTICAL METHODOLOGY**

#### **5.1. General Considerations**

All statistical evaluations will be conducted using SAS® version 9.4 or higher (SAS® Institute, Cary, North Carolina). All tables, figures and listings will be produced in landscape format.

Because of the small sample size no inferential statistical analyses or hierarchical testing are planned. Analysis will be descriptive in nature.

Each Part will be analyzed separately. Tables will have columns corresponding to or be stratified by study Parts. Select analyses, as specified in further sections, will be performed for pooled groups of Parts 1, 2 and 4 and Parts 3 and 5, representing similar RIP and PPS populations, i.e. symptomatic and asymptomatic-CS dependent subjects. In general, all data will be listed by study part, subject and visit/time point where appropriate. The total number of subjects under the stated population (N) will be displayed in the header of summary tables.

Data will be summarized using descriptive statistics for continuous variables. Unless otherwise specified, descriptive statistics will include number of subjects, mean, standard deviation, minimum, median and maximum. In case of  $n < 2$ , where  $n$  indicates the number of evaluable subjects at the particular time point, the standard deviation will not be calculated.. The statistic “Missing” will also be presented as the number of missing entries/subjects, if any

at that visit/timepoint, and presented as a summary statistic only when non-zero. The minimum and maximum statistics will be presented to the same number of decimal places as the original data. The mean and median will be presented to one more decimal place than the original data, whereas the standard deviation will be presented to two more decimal places than the original data.

In summary tables of categorical variables, counts and percentages will be used. The count [n] indicates the actual number of subjects with a particular value of a variable or event, which should always be less than or equal to the total number of subjects with non-missing value of the variable or event [M]. Percentage will be obtained by:  $\% = (n/M)*100$ . Unless otherwise stated, all percentages will be expressed to one decimal place.

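### The only follow-up-adjusted summary of on-study recurrences weights every subject equally whatever the follow-up, so its mean is unstable; a pooled person-time rate should be added

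*SAP*

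**What the plan says.** Section 5.4.9.10 of the SAP plans two summaries of recurrent pericarditis on study.

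- **A count table.** "The numbers of subjects with recurrent pericarditis episodes will be summarized by the number of recurrent episodes during the study". It takes no account of follow-up.
- **A duration-adjusted number of episodes.** For each subject this is the "number of recurrent episodes during the study divided by the study duration", with duration running "from the first dose of the study drug to study completion/discontinuation) in years". Then: "Duration-adjusted number of episodes will be summarized descriptively". By section 5.1, "descriptive statistics will include number of subjects, mean, standard deviation, minimum, median and maximum".

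On the population: "This analysis will be performed for the mITT population". Section 5.2.2 admits anyone who received at least one dose, and 5.4.9.10 sets no minimum follow-up. Neither section plans a rate formed from total episodes and total person-time.

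Follow-up differs by design. Under section 2.2, responders are "offered participation in an optional 18-week EP", in which "weekly administration of open-label KPL-914 may be continued for a total duration of 24 weeks". Subjects who do not enter it have about 6 weeks. Treatment Failures may be taken off study drug and are followed for safety for the rest of the 6 weeks. Section 3.1 foresees withdrawals. The baseline counterpart, the annual incidence of episodes in section 5.4.2, is also a ratio per subject, with disease duration as denominator.

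**The concern.** A ratio per subject gives a subject seen for 3 weeks the same weight as one seen for 24. One episode counts as 52/3 = 17.3 per year in the first and 52/24 = 2.17 per year in the second. In a small pilot reported Part by Part, one such subject can supply most of the mean, and its size then depends mainly on the week of exit. The median does not fill the gap, because it is 0 whenever fewer than half the subjects recur.

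Short follow-up is also tied to poor response, since the Extension Period is offered only to responders. If an episode itself leads to exit, small denominators go with episodes and the mean is pushed upward.

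At stake is a descriptive figure that later readers may take as the annual recurrence rate on treatment. Section 3.1 says the sample size was chosen partly to inform phase 3 planning. The similar form of the baseline incidence also invites a before-and-after comparison.

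**Working it through.** The SAP states no recurrence rate, so there is no planned figure to reproduce. The check compares two estimators on assumed data.

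**Inputs.** From the SAP: the ratio per subject and equal weighting (5.4.9.10, 5.1); 24 weeks with the Extension Period and about 6 without (2.2). Assumed: the number of subjects, the number of episodes and the week of exit. A year is taken as 52 weeks.

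**Formulas.** SAP mean = (1/N) × Σ(episodes / own years). Pooled rate = Σ episodes / Σ years.

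**Illustration: N = 25, 24 subjects with 24 weeks and no episode, one leaving at week w with one episode.** SAP mean = (52/w)/25. Person-years = (24 × 24 + w)/52.

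| Exit week | SAP mean per year | Person-years | Pooled per year | Ratio |
|---|---|---|---|---|
| 2 | 26/25 = 1.04 | 578/52 = 11.12 | 0.090 | 11.6 |
| 3 | 17.33/25 = 0.69 | 579/52 = 11.13 | 0.090 | 7.7 |
| 6 | 8.67/25 = 0.35 | 582/52 = 11.19 | 0.089 | 3.9 |
| 24 (equal follow-up) | 2.17/25 = 0.087 | 600/52 = 11.54 | 0.087 | 1.0 |

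The exact Poisson 95% limits for one event are 0.0253 and 5.572. Divided by 11.13 person-years they give 0.002 to 0.50 per year. The median is 0 in every row.

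**One Part, with an assumed 8 subjects and the same pattern.** SAP mean = (52/w)/8 and pooled = 52/(7 × 24 + w). For exit at week 2, 3 or 6 the mean is 3.25, 2.17 or 1.08 per year, against a pooled 0.31, 0.30 or 0.30.

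**The direction can reverse.** Take 20 subjects with 24 weeks and 5 with 6 weeks, with the only episode in a 24-week subject. SAP mean = (52/24)/25 = 0.087. Pooled = 52/(480 + 30) = 0.102. The mean is now 15% lower than the pooled rate.

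**Bias when an episode leads to exit.** Assume a constant true rate λ = 0.5 per year. Subjects leave at their first episode but are kept at least to week 6, others stay 24 weeks, and first episodes are counted. Let a = 6/52 and b = 24/52 years.

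- Expected SAP mean = (1 − e^(−λa))/a + ∫ from a to b of λe^(−λt)/t dt = 0.486 + 0.613 = 1.10 per year, about twice the truth.
- Expected pooled rate = (1 − e^(−λb)) / [a + (e^(−λa) − e^(−λb))/λ] = 0.206/0.415 = 0.50 per year.

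**What pooling costs.** Assume 20 responders at 0.2 per year for 24 weeks and 5 non-responders at 3 per year for 6 weeks.

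- Average subject's rate = (20 × 0.2 + 5 × 3)/25 = 0.76.
- Expected pooled rate = (20 × 0.2 × 24 + 5 × 3 × 6)/(480 + 30) = 186/510 = 0.36.
- Split by period, the pooled rate is (20 × 0.2 + 5 × 3) × 6/(25 × 6) = 0.76 in the Treatment Period and 0.2 in the Extension Period, so the selection becomes visible.

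**The case against.** The strongest case for the plan has five parts.

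- **The mean of ratios is a legitimate estimator.** If the rate is constant and follow-up does not depend on episodes, its expectation is the true rate and it is only less efficient. This stands. A reader might infer that the planned mean does not estimate an episode rate at all, and the documents do not support that. The bias arises only if episodes influence exit.
- **Distortion is not certain.** Unequal follow-up is built in, but a large inflation needs an episode in a subject with short follow-up. The SAP makes that plausible and does not say how often it would happen. The direction can also reverse. This stands.
- **The large ratios come from chosen scenarios.** Treatment Failures are followed to week 6. If that time counts as study duration, the week-6 figure (0.35 against 0.09) suits them better than those for week 2 or 3. Other withdrawals may leave sooner. This stands.
- **The outlier would be seen.** The maximum is reported, and the count table is untouched by follow-up. This is true and limits the harm, but neither gives a usable rate per year.
- **Pooling has its own slant.** It gives four times the weight to a responder kept for 24 weeks as to a subject with 6, and the Poisson interval assumes a common rate. Replacing the per-subject summary would also lose the parallel with the baseline incidence in section 5.4.2. This stands and shapes the fix.

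The rule against inferential analysis in section 5.1 is no bar to an interval, since sections 5.4.9.1 and 5.4.10.7 already plan 95% confidence intervals for Kaplan-Meier quantiles.

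**Conclusion.** The point holds in a limited form. Section 5.4.9.10 offers no person-time rate. Its only follow-up-adjusted summary has a mean that is unstable under the study's own follow-up pattern, and a median that is 0 whenever fewer than half the subjects recur. In the assumed 25-subject case the mean is 1.04, 0.69 or 0.35 per year as exit moves from week 2 to 3 to 6, while the pooled rate stays at 0.09. With an assumed true rate of 0.5 per year and exit at the first episode, but not before week 6, the mean is expected to be about double the truth.

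These sizes rest on assumed numbers of subjects, episodes and exit times, none of which the SAP gives. With equal follow-up nothing changes. The recurrence rate is not a primary endpoint (sections 4.1 and 4.2), and the SAP attaches no test or decision rule to it. The pooled rate is more stable but answers a slightly different question, so it belongs beside the planned summary and not in its place.

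**What to change.** Add to section 5.4.9.10: total episodes, total person-years and their ratio, with an exact Poisson 95% confidence interval, by Part and for the pooled groups (Parts 1, 2 and 4; Parts 3 and 5). Show episodes and person-years separately for the Treatment Period and the Extension Period. Keep the count table, and keep the per-subject summary for comparison with the baseline annual incidence in section 5.4.2.

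Add a footnote that the overall pooled rate gives more weight to responders who enter the Extension Period and that the interval assumes a common rate. State also whether safety follow-up after stopping study drug counts as study duration, since that sets the smallest denominators for Treatment Failures.

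The cost is a few lines of SAP text and one added table block. The totals use the same episode counts and durations, and the period split needs only episode dates and the Visit 7 date. No new data are collected.

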#### **5.4.9.11. Clinical Response**

Clinical Response is a composite endpoint defined at the visits when both pain NRS and CRP are assessed. A subject is defined to have clinical response if pain NRS assessment is  $\leq 2$  and CRP is normal ( $\leq 0.5$  mg/dL) at the same time.

Number and percentage of subjects with Clinical Response will be presented by visit through end of the study for the mITT population.

#### **5.4.10.1. Adverse Events**

Adverse Events will be coded using the Medical Dictionary of Regulatory Activities (MedDRA version 20.1) AE coding system for purpose of summarization.

An AE will be defined as treatment-emergent (TEAE) if its date/time of onset falls within the interval from the date/time of the first study drug administration until the end of study. If the date of AE onset coincides with the date of the first study drug administration and AE time is

not captured, AE will be considered treatment-emergent, unless the eCRF field “Did event start prior to first dose of study drug?” is checked as “Yes”.

An AE will be defined as treatment-related if its relationship to the study drug is recorded as Possibly Related or Related on the eCRF.

An overall summary of number and percentage of subjects with at least one AE, TEAE, serious TEAE, treatment-related TEAE, serious treatment-related TEAE, TEAE leading to discontinuation and TEAE leading to death will be presented. It will also include a summary of subjects by the highest severity of TEAE reported in the study.

A summary of the frequency (number and percentage of subjects) of TEAEs will be presented by system organ class and preferred term. Adverse events will also be analyzed by their severity (mild, moderate or severe) and relationship to study drug (related or not related).

A subject experiencing the same AE multiple times will be counted only once for that preferred term. Similarly, if a subject experiences multiple AEs (preferred terms) within the same system organ class then that subject will be counted only once for that system organ class. When summarizing by severity and relationship, only event with highest severity or relationship will be counted. All AEs will be presented in the descending order of total frequency by SOC and preferred terms within SOC.

These analyses will be performed by study part, but also for pooled groups of Parts 1, 2 and 4 and Parts 3 and 5 and total (all Parts combined)

All information pertaining to adverse events noted during the study will be listed by subject, detailing verbatim term given by the investigator, preferred term, system organ class, start date, stop date, severity, outcome, action taken and drug relatedness. Separate listings will be created for Serious TEAEs and TEAEs leading to study drug discontinuation.

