Subsequent weekly Study Drug administrations from Weeks 2 to 5 will be self-administered by the subject or administered by an adequately trained caregiver as an outpatient SC administration. A visiting study nurse will assess and record compliance with Study Drug administration at the subject's home as well as provide guidance and training on Study Drug administration as needed. At Week 6/End-of-Trial, Study Drug may be self-administered or administered at the Study site/clinic.

Investigators are encouraged to schedule subjects at the Study Site/Clinic for an in-person Interval Evaluation Visit during approximately Weeks 3-4 to assist the Investigator in the clinical management of the subject. However, this visit is not mandatory, and therefore not all subjects will have this visit.

Subjects reporting worsening of pericarditis symptoms or AEs may be brought in for an unscheduled visit at the Study Site/Clinic at any time during the Treatment Period, at the discretion of the Investigator. Any subject who is considered by the Investigator to be a "Treatment Failure" may be withdrawn from further Study Drug treatment at the discretion of the Investigator and receive rescue therapy for their pericarditis according to standard of care as per Investigator decision; these subjects will be followed for safety for the remainder of the 6- week Treatment Period. Subjects identified as "Treatment Failures" may be replaced at the discretion of the Sponsor in order to provide an adequate sampling of subjects completing the active Treatment Period.

During the Treatment Period, subjects will continue documentation of pericarditis treatment medication use as well as rescue (pain) medication use in the medication diary. Subject-reported pericardial pain evaluations will be performed on-site at the Study Site/Clinic and by weekly (and on Day 3) Investigator (or designee) telephone calls/virtual visits using a validated 11-point NRS instrument. A subject-reported QoL questionnaire will be administered at Visit 7 (Study Site/Clinic). Weekly blood samples for central laboratory

testing will be collected at the Study Site/Clinic or at a qualified laboratory site in the vicinity of the subject or by a visiting study nurse.

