#### **5.4.10.7. Pain/Rescue Medication Use**

Number and percentage of subjects who used Pain/Rescue medication at least once will be presented for the Treatment Period, Extension Period and entire study broken down by the medication type as captured on the eCRF (opioid analgesics, non-opioid analgesics, acetaminophen, other). Medication used at fixed doses and as needed (PRN) will be counted in analyses.

Time to first Pain/Rescue medication will be defined as the earliest study day when a rescue medication is taken post-baseline. For subjects who never took any rescue medication post-baseline, it will be censored at the study day of study completion/discontinuation. Kaplan-Meier estimates of the median, 25% and 75% percentiles of time to first rescue medication will be provided with 95% confidence intervals using the same methods as for time for CRP normalization (see Section [5.4.9.1](#)).

All Pain/Rescue medications will be listed.

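### TEAEs are summarised only as one crude whole-study percentage, although follow-up is about 6 or about 24 weeks depending on responder-only Extension Period entry

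*SAP*

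**What the plan says.** Section 5.4.10.1 of the SAP defines an adverse event as treatment-emergent if its onset "falls within the interval from the date/time of the first study drug administration until the end of study". The planned statistic is the number and percentage of subjects: "A summary of the frequency (number and percentage of subjects) of TEAEs will be presented by system organ class and preferred term". On grouping, it says: "These analyses will be performed by study part, but also for pooled groups of Parts 1, 2 and 4 and Parts 3 and 5", and it adds a total over all Parts. Treatment Period and Extension Period are not among the groupings. Section 5.1 defines a percentage as n/M, so time under observation does not enter.

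Section 2.2 makes follow-up unequal by design. Of subjects withdrawn from drug as Treatment Failures it says that "these subjects will be followed for safety for the remainder of the 6- week Treatment Period". Treatment Responders are, at the investigator's discretion, "offered participation in an optional 18-week EP", "in which weekly administration of open-label KPL-914 may be continued for a total duration of 24 weeks".

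Elsewhere the SAP allows for this structure. Drug exposure (5.4.8), changes in pericarditis medication (5.4.9.9), laboratory shifts (5.4.10.2) and local-read ECG shifts (5.4.10.5) are all broken down by period. Rescue medication use "will be presented for the Treatment Period, Extension Period and entire study" (5.4.10.7). Recurrent episodes are divided by study duration in years (5.4.9.10). Section 5.2.4 already defines an Extension Period Population.

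**The concern.** One numerator and one denominator mix subjects observed for about 6 weeks with subjects observed for about 24, and length of observation is tied to response. The resulting percentage depends on how many subjects continued as well as on how often events occur.

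The two periods also differ in kind. The Per-Protocol definition in 5.2.3 expects stable background medication during the Treatment Period, whereas 2.2 encourages weaning of NSAIDs, colchicine and corticosteroids in the Extension Period. Footnote v of Appendix 8.1 has subjects asked about adverse events weekly in the Treatment Period and monthly in the Extension Period. Feasibility of corticosteroid weaning is the primary objective for Parts 3 and 5, and safety is a secondary objective for all Parts, so it matters in which period an event arose. Section 3.1 says the sample size was set partly to inform phase 3 planning. A TEAE percentage without a fixed exposure time carries over poorly to a trial of another length.

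**Working it through.** The SAP states no TEAE rate and no Extension entry share, so there is no figure of its own to reproduce. What follows is an illustration on assumed inputs.

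**Inputs from the SAP (2.2).** Follow-up is about 6 weeks for non-entrants and about 6 + 18 = 24 weeks for subjects who continue to the end.

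**Assumed inputs.** A constant hazard λ to first TEAE, the same for all subjects; a 24-week risk of 40%; a share s of subjects who stop at 6 weeks, unrelated to adverse events.

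**Step 1, hazard.** λ = −ln(1 − 0.40)/24 = 0.5108/24 = 0.02128 per week.

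**Step 2, 6-week risk.** 1 − exp(−6 × 0.02128) = 1 − 0.880 = 12.0%.

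**Step 3, planned percentage.** Crude = (1 − s) × 40% + s × 12.0%.

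| s, share stopping at 6 weeks | Crude TEAE percentage |
|---|---|
| 10% | 0.9 × 40 + 0.1 × 12.0 = 37.2% |
| 20% | 0.8 × 40 + 0.2 × 12.0 = 34.4% |
| 40% | 0.6 × 40 + 0.4 × 12.0 = 28.8% |
| 50% | 0.5 × 40 + 0.5 × 12.0 = 26.0% |

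**Step 4, other event rates.** Start from an assumed 6-week risk p6, so that the 24-week risk is p24 = 1 − (1 − p6)^4. With u the share entering the Extension Period, crude = u × p24 + (1 − u) × p6, and mean follow-up is 6 + 18u weeks.

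| p6 | u = 0% | 50% | 75% | 90% | 100% |
|---|---|---|---|---|---|
| 5% | 5.0 | 11.8 | 15.2 | 17.2 | 18.5 |
| 10% | 10.0 | 22.2 | 28.3 | 32.0 | 34.4 |
| 20% | 20.0 | 39.5 | 49.3 | 55.1 | 59.0 |
| 30% | 30.0 | 53.0 | 64.5 | 71.4 | 76.0 |
| Mean follow-up (weeks) | 6 | 15 | 19.5 | 22.2 | 24 |

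Two Parts with the same hazard (p6 = 20%) but 50% and 90% entry would show 39.5% and 55.1%.

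**Step 5, the alternatives.** A Treatment Period percentage equals p6 whatever u is, apart from withdrawals before 6 weeks. For the exposure-adjusted rate, expected time at risk to first event over follow-up T is (1 − exp(−λT))/λ, so subjects with a first event divided by time at risk equals λ at every u. Per subject-year (52.18 weeks) that is 0.45, 0.92, 1.94 and 3.10 for p6 = 5%, 10%, 20% and 30%.

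**Step 6, scale.** About 40 subjects over five Parts average 8 per Part (allocation is not stated). A contrast of 40% (all enter) with 28.8% (40% stop at 6 weeks) is 0.40 × 8 = 3.2 against 0.288 × 8 = 2.3 subjects. The standard error of a 35% proportion with n = 8 is √(0.35 × 0.65/8) = 0.17, or 17 points, which exceeds the 11-point gap.

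**The case against.** Whole-study subject incidence is an accepted descriptive safety summary for an open-label pilot. Section 5.1 rules out inferential analysis, and no between-Part comparison of TEAEs is planned, so no error rate or decision rule is affected. Step 6 shows that within a Part the distortion can be less than one subject. The illustration assumes a constant hazard and stopping unrelated to adverse events; if first events cluster in the first 6 weeks the gap shrinks, and if all occur there it vanishes. All of this stands, and it limits the weight of the point.

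Three stronger readings are tempting, and the SAP does not support them:

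- A reader might infer that the percentage refers to no defined period. It does: 5.4.10.1 fixes the window for each subject as first dose to end of study. The difficulty is that the window's length varies between subjects.
- A reader might infer that Parts cannot be compared. That holds only if Extension entry or discontinuation differs by Part. The SAP gives no entry shares, and with equal entry and retention follow-up length would not distort the comparison.
- A reader might infer that events during weaning cannot be told apart from early events. The listings carry adverse event start and stop dates (5.4.10.1), dosing dates (5.4.8), and Extension entry with completion or withdrawal dates (5.4.1). With about 40 subjects the split can be rebuilt by hand. What is missing is the summary table.

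The objection does not remove the core. In a descriptive study the summary tables are the result, and the single percentage stays ambiguous even when all Parts have equal entry.

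**Conclusion.** The point holds as a matter of interpretation. The planned TEAE tables give one crude percentage that mixes about 6 and about 24 weeks of observation, so it estimates neither a 6-week nor a 24-week risk. Between Parts the figures may not be comparable, conditional on differing Extension entry or discontinuation. The tables do not show whether events arose in the first 6 weeks or during weaning.

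Under an assumed constant hazard and 24-week risk of 40%, the crude figure runs from 37.2% to 26.0% as the share stopping at 6 weeks goes from 10% to 50%. These sizes rest on assumed hazards and assumed entry shares. The absence of a period split and of person-time rests on the text alone. The SAP makes one or the other allowance for several other outcomes and gives no reason for leaving adverse events out.

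**What to change.** In 5.4.10.1, present the TEAE summaries for three windows, as 5.4.10.7 already does for rescue medication:

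- the Treatment Period, in the safety population;
- the Extension Period, in the Extension Period Population, labelled as selected responders;
- the entire study, as now planned.

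State the boundary. For entrants, TEAEs with onset from the first study drug dose at or after Visit 7 belong to the Extension Period and earlier ones to the Treatment Period. For non-entrants, all TEAEs up to the end of their follow-up belong to the Treatment Period. The convention in 5.4.9.9, which ends the Treatment Period of non-entrants at the last dose, should not be borrowed. Section 2.2 keeps Treatment Failures under safety follow-up after drug is stopped, and their later events would fall in neither period table.

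In the overall summary, add an exposure-adjusted rate: subjects with a first event per subject-year at risk. Event counts per subject-year are optional; they include repeats, so one subject could dominate in a small Part.

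The cost is re-running existing table shells by period and adding one column. No new data are needed. The downside is a few more tables with small counts, and the Extension Period table describes responders only, so it does not by itself make Parts comparable.
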